## **18.0 Potential Benefits to Subjects**

*18.1 Describe the potential benefits that individual subjects might experience from participating in the research. Include the probability, magnitude, and duration of the potential benefits, as this will be useful to the IRB's risk:benefit analysis. Do not include benefits to society or others. Do not*

*list monetary or non-monetary compensation for participation, as this is not a benefit These should be included in section 2 or 3 of this document:*

Participants will gain information about their body composition, resting metabolism, fitness, and general health. They will also learn about healthy weight gain regimens and how to properly perform strength/resistance training exercises.

*18.2 If applicable, specify that there are no anticipated direct benefits for participants:*

N/A

## **19.0 Data Management and Confidentiality**

*19.1 Describe procedures that you will use for quality control to ensure validity of collected data:*

Drs. [name] and [name] have extensive experience performing data collection on all of the procedures outlined in this proposal as does the study coordinator, [name]. They will ensure all study personnel, including graduate students, will be properly trained to perform all procedures according to standard protocol. Specific quality control measures will be employed to ensure valid indirect calorimetry data are collected during the RMR, walking economy and VO2max tests; These standards are included on data collection sheets for use by members of the study team.

*19.2 Describe any existing data or biospecimens you will obtain as part of this study. Include:*

- *Variables or samples to be obtained*
- *Source of the data or specimens*
- *Your authorization to access or receive the data or biospecimens*
- *Whether the data or biospecimens are publicly available*
- *Whether the data or specimens you receive will contain identifiers*

N/A

*19.3 Describe the steps that you will take to handle and secure study data during data collection, storage, use, and transmission. Include information about training of study staff, authorization of access, password protection, encryption, physical controls, certificates of confidentiality, separation of identifiers and data, etc.:*

We will do everything that we can to make sure that study records are kept private. Each participant will be assigned a unique participant code as explained in section 9.4. All data recording sheets and spread sheets will use the subjects' study code. They will not contain the participants' name or date of birth. These will be compiled in a patient research file/chart and stored in a locked file cabinet organized by their unique study code. Their name will be listed only on the phone screening log (which is to be blackened out after they are assigned a participant code), informed consent and on a master participant list that includes the randomization key. The master participant list will be kept in a separate electronic file than the data files; both will be password-protected. The study consents will be kept together in a separate file in a separate location in a locked office. Only authorized study personnel will have access to study data. Results of the study may be published and/or presented at professional conferences. The participants' name or other personal information that would identify them will not be used. All blood collected and post-processed serum and plasma samples will be labeled with the participants unique study code (plus the study visit and date and time of sample collection) and stored in a secure freezer in a locked laboratory until analysis as mentioned in section 9.2. Archives may be kept for up to five years following study analysis. Training of study personnel including graduate students on procedures to ensure secure collection and storage of study data will occur before study initiation.

*19.4 For multi-site studies, describe how data or specimens will be handled and secured for each site (e.g., central or disseminated data storage, data coordinating center):*

N/A

*19.5 Describe the plan for data disposition following the conclusion of the study (e.g., long term maintenance of data, data destruction methods).*

- *What information will be included in the long term storage of data or specimens?*
- *How long will the data or specimens be stored?*
- *Where and how data or specimens will be stored?*
- *Who will have access to the data or specimens during long term storage?*

- *Who is responsible for receipt or transmission of the data or specimens?*
- *How will data or specimens be shared or transported?*
- *When and how will personal identifiers be destroyed?*

Telephone screening forms (that contain participants' names) and the Eating Attitudes Tests will be shredded immediately after all study participants are recruited. Personal information, primary and secondary endpoints and safety data will be kept indefinitely in a secured electronic location by the PI and co-investigator. Personal information will be kept in a separate file than de-identified data. Blood and urine samples labeled with the patients' unique study code may be stored in a laboratory freezer in a locked laboratory for up to five years following the completion of the analyses; only authorized study personnel will have access to freezer samples. The PI will be responsible for transmission of all data or achieved specimens. Although it is not anticipated that any data will need to be transported or shared, this would be done only using de-identified data with samples sent using a secure mechanism.

## 20.0 Provisions to Protect the Privacy Interests of Subjects

20.1 *Describe the steps that you will take to protect subjects' privacy interests.*  
"Privacy interest" refers to a person's desire to place limits on with whom they interact or to whom they provide personal information (e.g., collecting the minimal amount of private information required to complete the study, protecting the data once it is obtained):

To ensure privacy interests of all interested and enrolled participants, only the minimal amount of personal information and health history will be obtained using a standard health history form; this form has been used by [name] for the past 17 years. This data will be kept in participant files labeled with only the participants' study code in a secured file in a locked room. The data for all participants who do not participate in the study will be destroyed by shredding. The data for participants who do enroll will be entered into an electronic data base using the participants assigned unique study code. Any and all original data collection sheets with the participants' name or identifying information will also be destroyed following entry into the database.

20.2 *Describe steps that you will take to make subjects feel at ease with the research situation in terms of the questions being asked and the procedures being performed. "At ease" does not refer to physical discomfort, but the sense of intrusiveness a subject might experience in response to questions, examinations, and procedures (e.g., use of a same*

*gender investigator to place sensors on the torso, a private changing area if clothing must be changed, sensitivity when discussing pregnancy testing with subjects, making it clear on surveys that participants can discontinue at any time, not asking questions about private or sensitive issues unless necessary for the research):*

All questionnaires and anthropometric testing will be performed by trained research personnel in a private setting. Assignment of same-sex researchers will be employed if necessary; however, all study personnel will be trained to exhibit professional behavior and sensitivity when collecting personal health or medical data or when performing body composition or other testing.

*20.3 Describe how you plan to access existing sources of information about the subjects (e.g., medical records, grades) and how you will protect participant privacy through the data security plan:*

N/A

*20.4 Describe any required reporting that might occur as a result of your research questions, study populations, and data collection methods. Examples for Virginia and Virginia Tech include:*

- *Any suspicions (e.g., circumstantial, disclosed) of child abuse (physical, emotional, sexual) and neglect*
- *Sexual discrimination and/or sexual violence that involves a student*
- *Disclosure or signs of intention to harm oneself (i.e., suicidal ideation and/or plan)*
- *Disclosure or signs of desire to harm others (i.e., homicidal ideation and/or plan)*
- *Suspected abuse, neglect or exploitation of vulnerable adults (e.g., individuals with a disability, elderly persons)*

N/A

## **21.0 Provisions to Monitor the Data to Ensure the Safety of Subjects**

*Safety monitoring is required when research involves greater than minimal risk and is sometimes appropriate for other studies.*

*21.1 Describe:*

- *The plan to periodically evaluate the data collected regarding both harms and benefits to determine whether subjects remain safe (e.g., periodic reporting to the IRB, establishing a data monitoring committee, reporting data monitoring committee findings to the IRB and the sponsor).*
- *What data you will review, including safety data, unexpected events, and data that show the ability to produce the intended results.*
- *How the safety information will be collected (e.g., with case report forms, at study visits, by telephone calls with subjects).*
- *The frequency of data collection, including when safety data collection starts.*
- *Who will review the safety data and with what frequency.*
- *The statistical tests for analyzing the safety data to determine whether harm is occurring.*
- *Any conditions that will trigger an immediate suspension of the research (e.g., a serious adverse event).*

The data safety monitoring plan (DSMP) for this study focuses on close monitoring by the principal investigator (PI) and research staff along with prompt reporting of excessive adverse events and any serious adverse events (AEs) to the Institutional Review Board. All serious AEs will be reported by the PI within 48 hours of occurrence to the IRB and the sponsor.

The safety data monitored will include data related to the blood collections, exercise testing and the supervised resistance training sessions. Specific safety data include any reports of pain, excess swelling, redness or bruising after the blood draws at the needle insertion site, feelings of light headedness, chest tightness or pain or fatigue on exertion during exercise testing procedures, and symptoms of muscle soreness, joint pain, stiffness or unexpected events/issues during the 12 weeks of resistance training. Data will be collected and documented in the participant's chart if a situation arises or when observed by a member of the research team or reported by a participant during a study visits or during supervised resistance training sessions using a general TBD incident reporting form. Safety data will also include excessive changes in blood pressure or weight gain that will be measured during each scheduled study visit, and changes in blood glucose or serum cholesterol that will measured at the beginning and end of the study.

The Project Coordinator ([name].) will be responsible for assembling the data and producing these reports as well as assuring that all parties obtain copies of these reports. Reports will be submitted annually to the VT IRB for review.

Safety Data collection will start when the first participant is screened and enrolled. The study team will be informed to discuss any observed or reported unusual, excessive or unexpected events immediately with the PI. The PI and/or study coordinator will review study charts and ongoing data collected on all participants on a weekly basis to ensure

safety. In our small study, it is unlikely that use of statistics would be necessary to determine if excessive events were occurring; however, paired t-tests could be used if appropriate (i.e. for blood pressure, blood glucose or serum cholesterol data). We do not anticipate that there would be any specific events, other than the unexpected, that would trigger the suspension of our study,

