#### Safety Endpoints

Excess weight gain (>1.5 lb/wk)

Change in and absolute values for several health outcomes including blood pressure, serum cholesterol, fasting and 24-hour glucose concentration and hydration status

Excessive muscle soreness and/or pain

Muscle or joint injury

General fatigue

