**Walking Economy and Aerobic capacity (VO2max):** A graded exercise test will be performed on a treadmill to assess aerobic fitness via indirect calorimetry (Parvo Medics TrueOne 2400). Heart rate will be measured during the test by a heart rate strap and sensor. The exercise test will consist of walking or running on the treadmill starting at a self-selected pace with the grade or speed increasing every min until the participant reaches volitional exhaustion and can no longer continue. The test will begin with a walking economy test in which the participant walks for 4-minutes at 2.5, 3 and 3.5 mph. The last two minutes of oxygen consumption and carbon dioxide production data will be used to determine metabolic economy (ml oxygen consumed per kg body weight per minute relative to the set work performed). Following cumulation of the standard economy test, the workload will be increased each minute by increasing treadmill speed or grade by 0.5 mph or 2.5%, respectively until the participants reach volitional exhaustion. The entire exercise testing protocol (metabolic economy plus VO2max) will last 20-25 minutes.

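### Two of the five safety endpoints in Section 4.2, general fatigue and excessive muscle soreness or pain, have no systematic collection or grading in Section 21.1

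*Combined protocol and SAP*

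**What the plan says.** Section 4.2 has five safety endpoint entries. Two are symptoms with no definition, scale or assessment time: "Excessive muscle soreness and/or pain" and "General fatigue". By contrast, weight gain in the same list has a numerical cut-off of more than 1.5 lb per week.

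Section 21.1 sets out the safety data to be monitored. After blood-draw reactions, light-headedness and chest symptoms, it lists "fatigue on exertion during exercise testing procedures, and symptoms of muscle soreness, joint pain, stiffness or unexpected events/issues during the 12 weeks of resistance training". Entries are made in the chart when a situation arises, when staff observe something, "or reported by a participant during a study visits or during supervised resistance training sessions using a general TBD incident reporting form".

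Table 1 (Section 8.1) schedules no rating of fatigue or soreness at baseline or at weeks 3, 7 or 11. It places aerobic capacity, walking efficiency and strength testing at baseline and week 11 only. Section 8.2 runs the treadmill test "until the participant reaches volitional exhaustion and can no longer continue". The same section holds a weekly assessment during one training session, to check compliance and weight progress.

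**The concern.** Section 4.2 names what is to be judged and Section 21.1 says what is gathered, and for these two endpoints the two do not line up. The fatigue of interest is what may build up over weeks of surplus feeding and hard training, but the only fatigue item named belongs to laboratory tests at the two ends of the study. For soreness, which Section 17.1 calls the most likely training risk, the endpoint turns on the word *excessive*, and nothing says when a report becomes excessive.

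If the plan is followed as written, the record for both endpoints will depend on who speaks up and who writes it down. Participants know whether they are in the peanut or the non-peanut group (Section 8.2), so voluntary reporting could differ between arms for reasons unrelated to symptoms. Any safety summary for these endpoints would then be hard to interpret, even as plain description.

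**Working it through.** There is no figure in the plan to reproduce, so the check is a comparison of the sections, with a few simple counts.

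**1. General fatigue**
- Section 4.2: general fatigue, with no instrument and no timing.
- Section 21.1: fatigue is named once, on exertion, during exercise testing.
- Table 1: exercise testing falls at 2 of the 4 testing visits (baseline and week 11). One of these precedes the intervention. A fatigue rating is scheduled at 0 of the 4.
- Training between those visits: 10 weeks × 3 sessions per week = 30 sessions, with no named fatigue item.
- Remaining route: the catch-all for unexpected events in Section 21.1. General fatigue can be charted there, but nobody is asked about it.

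**2. Muscle soreness or pain**
- Section 4.2: counts only excessive soreness or pain.
- Section 21.1: takes in any soreness, joint pain or stiffness, without a grade.
- Any soreness includes excessive soreness, so the relevant events fall within what may be recorded. Without a grade, however, they cannot be picked out by a consistent rule.
- The escalation routes rest on the same undefined word. Staff bring excessive events to the principal investigator (Section 21.1), and participants are told to report excessive strain (Section 17.1).

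**3. Method of collection**
- Section 21.1 relies on observation or participant report, on an incident form still to be designed.
- The protocol template's prompt in Section 17.2 gives, as an example, asking participants at regular intervals to rate how they feel from 1 to 10. The answer refers back to Section 17.1, which contains no such rating.

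**4. Share of the safety endpoints affected**
- 2 of the 5 entries in Section 4.2. Weight and blood pressure are measured at each study visit, and glucose and cholesterol at the beginning and end, so this point does not extend to them.

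**5. Length of training**
- Section 21.1 refers to 12 weeks of training. Sections 1.0, 5.1, 8.1 and 11.1 give 10. The passages must be reconciled.

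**The case against.** The strongest reply is that the plan casts a wide net and escalates what is serious. Staff supervise training three days a week, unusual or excessive events go to the principal investigator at once, and charts are reviewed weekly. The list in Section 21.1 is open-ended, and the incident form and other collection sheets, which are not in these documents, may grade severity. Much of this stands, and it rules out two stronger readings.

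A reader might infer that the two endpoints are not measured at all. The documents do not support that. Excessive soreness is a subset of what Section 21.1 collects, it has a reporting route, and general fatigue can enter through the catch-all. The defect is the lack of a definition, a grade and a routine question.

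A reader might also infer that the fatigue item is met by everyone by design, because the treadmill test ends in exhaustion. That over-reads Section 21.1. Recording is triggered by events and is not a checklist scored at each test. The item sits in a list of warning symptoms, and Section 17.1 has staff watch for signs of problems. Exercise testing also includes walking stages at 2.5, 3 and 3.5 mph, where fatigue is not the planned end. Deleting the item could lose a warning sign.

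The reply is also right that Section 21.1 plans no comparison of soreness or fatigue between arms, and that the documents give no expected symptom rates, so no event counts can be projected.

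What the reply does not answer is why two named endpoints should rest on unsolicited reports when a weekly contact already exists. A form still to be written cannot be taken as the missing definition.

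**Conclusion.** The concern holds as a mismatch between Section 4.2 and Section 21.1. Two of the five safety endpoint entries lack systematic capture. General fatigue has no named item during about 30 training sessions, and excessive soreness has no grade from which it could be derived consistently. This should be changed. It affects descriptive safety reporting and not any efficacy conclusion.

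The conclusion assumes that no uploaded form outside these documents already schedules and grades the two symptoms. If one does, the remedy reduces to citing it in Sections 4.2 and 21.1. The difference between 12 and 10 weeks is a separate inconsistency and adds no weight to the main point.

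**What to change.** Reconcile Section 21.1 with Section 4.2 as follows:

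- At the existing weekly assessment, ask every participant in both arms for a 0-10 rating of general fatigue and a 0-10 rating of muscle soreness/pain. Add both to Table 1 and to the data collection forms.
- Have the investigators set, before data are collected, the rating that counts as excessive.
- Summarise both ratings descriptively by arm. No test is needed.
- Keep exertional symptoms during exercise testing as a separate warning-sign item, with a note that expected exhaustion at the end of the maximal test is not in itself an event.
- Reconcile the stated length of training in Section 21.1 with the other sections.

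The cost is two short items a week. Assuming 10 weekly assessments, that is 2 × 10 = 20 ratings per participant, or 20 × 32 = 640 for the planned sample and 20 × 40 = 800 if all 40 are enrolled and complete. It adds no visit and changes nothing in the intervention.

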## 22.0 Compensation for Research Related Injury

*22.1 If the research involves more than minimal risk to subjects, describe the available compensation in the event of research-related injury, if any:*

Participants will not be provided any form of compensation for medical treatment or other damages (for example lost wages, time lost from work, etc.). If a participant becomes injured or sick from the research, they will be referred to a clinic or to their personal health care provider. Medical treatment may be provided at their expense or at the expense of their insurance company.

*22.2 Provide a copy of contract language, if any, relevant to compensation for research-related injury. At Virginia Tech, this is most common for sponsored research:*

I do not believe this applies

## 23.0 Economic Burden to Subjects

*23.1 Describe any costs that subjects might be responsible for because of participation in the research, including any uncompensated costs for items such as transportation, missed work, and childcare:*

The participant will be responsible for costs that may include purchase of athletic clothes or shoes to participate in the resistance training sessions or the uncompensated cost that might include transportation, missed work or childcare.

## 24.0 Consent Process

*24.1 Indicate the process by which you will obtain consent for study participation. Please upload all consent, parental permission, and assent*

*forms, documents, and scripts referenced in this section to Protocol Management.*

*Describe the following:*

- *Where the consent process will take place (e.g., clinic waiting area, classroom, online)*
- *The time interval between sharing the consent information with the prospective subject and obtaining consent. For lab, interview, and focus group studies, the Virginia Tech IRB prefers that subjects have at least 24 hours to review the consent form and study information before the appointment where consent will be obtained. For simple online survey studies, you can typically present the consent information immediately before subjects begin participation.*
- *If applicable, processes to ensure ongoing consent or assent (e.g., for multiple sessions; for research in which a minor will turn 18 during the study; for longitudinal research with minors who will later be asked to provide or affirm their assent).*
- *Please review “SOP: Informed Consent Process for Research (HRP-090)” for recommended procedure. Describe your process, being sure to include:*
  - *The name and role of all study personnel who will be trained and certified by the PI to conduct the consent process*
  - *The time that will be devoted to the consent discussion*
  - *Steps that you will take to minimize the possibility of coercion or undue influence*
  - *Steps that you will take to gauge or ensure the subjects’ understanding*

Participants will be first screened over the phone. The phone screening will include an overview of the study, the time commitment and the possible risks to participation. After explaining the study and before conducting the phone screen, a study team member will describe the purpose of the phone screen and what type of data will be collected, and then ask that the participant provide verbal permission to conduct the phone screening. They will also be informed that they may refuse to answer any and all questions. An informed consent form will be emailed (or mailed) to the participant following the phone screening and at least 24 hours in advance of coming to the laboratory for the screening visit.

At the start of the screening visit, a team member will provide potential participants with a written copy of the study consent form and review the document with the participant. Participants will be encouraged to ask questions and seek clarification during the phone screening. The participant will then be encouraged to ask questions before providing written consent. As much time as necessary will be devoted to address participant concerns. Once the participant is ready to sign, he/she will be

allowed to sign in a private room near the door where they may also exit the lab if they no longer wish to participate. Screening and informed consent will be performed by the study coordinator or the doctoral student in charge of the study ([name]). Participants will be encouraged to ask questions and seek clarification during the phone screening and before signing the consent at the beginning of the laboratory screening visit.

These steps including time to review the consent before the screening visit, time with study staff to review the protocol and address concerns, and time to sign the consent in a private setting and close to a laboratory exit will help minimize the possibility of coercion or undue influence.

To help gauge the participant's understanding, the team member will ask the participant to explain the study, how often they will be asked to consume the peanut or high-carbohydrate snacks, how many times a week they would need to come to the lab to resistance train and how many lab visits are expected.

